12.6.2.2 Nicotine and Cotinine Concentrations

The concentrations of nicotine and cotinine will be listed and summarized. During confinement, the evening concentration levels at 08:00 PM is considered. Baseline is the assessment at 08:00 PM to 09:30 PM on Day 0. Line graphs of the nicotine and cotinine concentration profiles across all study days showing mean and 95% CI of percent change from baseline will also be produced.

Nicotine and cotinine concentrations at each post-baseline timepoint will be analysed in the log space using an ANCOVA model with terms for log-transformed baseline concentration, sex, average daily mCC consumption over the last 4 weeks as reported during screening, time point, product, and the interaction term between time point and product. No adjustment will be made for multiple comparisons.

The SAS code described in Section 12.6.1.3 "Sensitivity Analysis" will be used for the analysis of nicotine and cotinine.

Geometric LS means for each product along with the ratio (THS 2.2 Menthol : mCC) and 95% CI will be presented in the tables.

All figures, summaries and analyses will be performed on the PP Set and FAS by randomization arm.

The data will be presented in the below outputs:

TFL number	Title
FIGURES	
15.1.2.1.1	Plasma Nicotine and Cotinine Profile (ng/mL) over the 90 Days Arithmetic Mean and 95% CI for Percent change from baseline – PP Set

TFL number	Title
15.1.2.1.2	Plasma Nicotine and Cotinine Profile (ng/mL) over the 90 Days Arithmetic Mean and 95% CI for Percent change from baseline – FAS
TABLES	
15.2.4.19.1	Descriptive Statistics of Plasma Nicotine and Cotinine Concentrations (ng/mL) – PP Set
15.2.4.19.2	Descriptive Statistics of Plasma Nicotine and Cotinine Concentrations (ng/mL) – FAS
15.2.4.20.1	Analysis of Plasma Nicotine and Cotinine Concentrations (ng/mL) over the 90 Days – PP Set
15.2.4.20.2	Analysis of Plasma Nicotine and Cotinine Concentrations (ng/mL) over the 90 Days – FAS
LISTINGS	
15.3.3.3	Listing of Plasma Nicotine and Cotinine Concentrations

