12.6.1 Primary Analyses

12.6.1.1 Analysis of Biomarkers of Exposure for Primary Objectives

The BoExp (COHb in blood and urinary concentrations of MHBMA, 3-HPMA, S-PMA and Total NNAL) used for the primary analysis will be described as detailed in Section 12.1.3 “Descriptive Statistics”. The listing of the COHb data will have a flag for whether a subject’s COHb was <2%.

The baseline is as defined in Section 12.1.4 “Definitions for Statistical Data Analysis”.

The primary endpoints will be log-transformed (base_e) prior to analysis. The analysis will compare the evening COHb level (20:00-21:30) at Day 5; and urinary concentrations of MHBMA, 3-HPMA and S-PMA adjusted for creatinine on Day 5 and urinary concentrations of Total NNAL adjusted for creatinine on Day 90 Visit between the THS 2.2 Menthol and mCC arms for the PP Set. An analysis of covariance (ANCOVA) (Snedecor and Cochran 1982) model will be used with terms for the log-transformed baseline value, sex, average daily mCC consumption over the last 4 weeks as reported during screening and randomization arm.

The SAS code to be used for the THS 2.2 Menthol and mCC data is shown below:

```
Proc glm data=_data_ ;
  Class randomization_arm sex cigarette_cons;
  Model log_biomarker = log_baseline sex cigarette_cons
    randomization_arm;
  Lsmean randomization_arm / pdiff =control('mCC') alpha=0.05 cl;
  Run;
```

The least squares (LS) means and estimate of the difference and the 95% CI will be back-transformed. The geometric LS means for each randomization arm along with the ratio (THS 2.2 Menthol : mCC), two-sided 95% CI and one-sided p-value will be presented in the tables. THS 2.2 Menthol : CC effects will be graphed in a forest plot.

All figures, summaries and analyses will be performed on the PP Set. Additional descriptive statistics will be provided within the secondary analysis.

The data will be presented in the below outputs:

TFL number	Title
FIGURES	
15.1.1.1	Forest Plots of Statistical Analysis of Biomarkers of Exposure for Primary Objective – PP Set
15.1.1.2	Biomarker of Exposure for Primary Objective Arithmetic Mean and 95% CI for Percent Change from Baseline – PP Set
TABLES	
15.2.3.1.1	Analysis of COHb, MHBMA, 3-HPMA, S-PMA and Total NNAL on Day 5/90 Visit for THS 2.2 Menthol versus mCC for the Primary Objective – PP Set
15.2.4.1.1	Descriptive Statistics of Blood COHb (%) – PP Set
15.2.4.1.1.1	Descriptive Statistics of Blood COHb (%) by Sex – PP Set

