12.6.1.3 Sensitivity Analysis

As a sensitivity analysis, the ANCOVA model described in Section 12.6.1.1 "Analysis of Biomarkers of Exposure for Primary Objectives" will be repeated for the PP Set at Day 5 and Day 90 data by means of a mixed model approach, without the LOCF data imputation described in Section 12.1.5 "Handling of Dropouts or Missing Data (including outside the limits of quantification)". Any data outside of the allowed time window (see Table 18: Assessment Windows) on Days 5 and 90 will be excluded from the analysis.

The SAS code to be used for the THS 2.2 Menthol and mCC data is shown below:

```
Proc mixed data=_data_;
  Class randomization_arm sex cigarette_cons;
  Model log_biomarker = log_baseline sex cigarette_cons
    randomization_arm;
  Lsmean randomization_arm / pdiff =control('mCC') alpha=0.05 cl;
  Run;
```

An additional sensitivity analysis will be produced for the primary analysis, summaries and graphs of the COHb, MHBMA, 3-HPMA, S-PMA and Total NNAL will be repeated for the compliant population for THS 2.2 Menthol vs mCC. The analysis will use the same model as described in Section 12.6.1.1 "Analysis of Biomarkers of Exposure for Primary Objectives"

The data will be presented in the below outputs:

TFL number	Title
FIGURES	
15.1.1.3	Biomarker of Exposure Arithmetic Mean and 95% CI for Percent Change from Baseline – Compliant Population
TABLES	
15.2.3.1.2	Sensitivity Analysis of COHb, MHBMA, 3-HPMA, S-PMA and Total NNAL on Day 5/90 Visit for THS 2.2 Menthol versus mCC for the Primary Objective using Mixed Model – PP Set
15.2.3.1.3	Sensitivity Analysis of COHb, MHBMA, 3-HPMA, S-PMA and Total NNAL on Day 5/90 Visit for THS 2.2 Menthol versus mCC for the Primary Objective – Compliant Population
15.2.4.1.3	Descriptive Statistics of Blood COHb (%) – Compliant Population
15.2.4.2.3	Descriptive Statistics of MHBMA in 24-hour Urine Collection – Compliant Population
15.2.4.3.3	Descriptive Statistics of 3-HPMA in 24-hour Urine Collection – Compliant Population
15.2.4.4.3	Descriptive Statistics of S-PMA in 24-hour Urine Collection – Compliant Population
15.2.4.5.3	Descriptive Statistics of Total NNAL in 24-hour Urine Collection – Compliant Population

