12.6.2.1 Analysis of Biomarkers of Exposure for Secondary Objectives

The BoExp for the secondary objectives are exhaled CO and total 1-OHP, Total NNN, 4-ABP, 1-NA, 2-NA, o-tol, CEMA, HEMA, B[a]P, HMPMA, S-BMA and NEQ (all analysed from a 24-hour urine collection) at Day 5 and Day 90 will be described as reported in Section 12.1.3 "Descriptive Statistics". Urine parameters will be analyzed as concentration adjusted for creatinine and the quantity excreted in urine over 24 hours. In addition the quantity excreted in urine over 24 hours for MHBMA, 3-HPMA, S-PMA and Total NNAL will also be presented as above.

All BoExp apart from CO breath test will be analyzed in the log scale.

BoExp will be analyzed using the same model described in Section 12.6.1.1 "Analysis of Biomarkers of Exposure for Primary Objectives". No adjustment will be made for multiple comparisons. For all BoExp, if the results from the Day 5 analysis are significant (one-sided p-value ≤ 0.025) then the statistical significance will be evaluated for the results of the analysis at Day 90 values. LS means for each product along with the ratio (THS 2.2 Menthol : mCC) and 95% CI will be presented in the tables. Forest plots of the ratios and 95% CI will also be produced.

BoExp will also be examined to compare the reductions in THS 2.2 Menthol vs. SA using the same methodology as above for the PP Set. In addition, the sensitivity analyses described in Section 12.6.1.3 "Sensitivity Analysis" for the biomarkers of exposure for primary objectives will be repeated for the biomarkers of exposure for secondary objectives.

The data will be presented in the below outputs:

TFL number	Title
FIGURES	
15.1.1.2	Biomarker of Exposure Arithmetic Mean and 95% CI for Percent Change from Baseline – PP Set
15.1.1.4	Biomarker of Exposure Arithmetic Mean and 95% CI for Percent Change from Baseline – FAS
15.1.1.5	Forest Plots of Statistical Analysis of Biomarkers of Exposure for Secondary Objective – PP Set
TABLES	
15.2.3.2	Analysis of COHb, MHBMA, 3-HPMA, S-PMA, and Total NNAL on Day 5/90 Visit versus mCC and SA for the Secondary Objective – PP Set.

TFL number	Title
15.2.3.3	Analysis of COHb, MHBMA, 3-HPMA, S-PMA, and Total NNAL on Day 5/90 Visit versus mCC and SA for the Secondary Objective – FAS.
15.2.3.4	Analysis of Additional Biomarkers of Exposure versus mCC and SA on Day 5/90 Visit– PP Set.
15.2.3.5	Analysis of Additional Biomarkers of Exposure versus mCC and SA on Day 5/90 Visit– FAS.

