15.2.3.6	Analysis of Additional Biomarkers of Exposure versus mCC and SA using Mixed Model on Day 5/90 Visit – PP Set
15.2.3.7	Analysis of Additional Biomarkers of Exposure versus mCC and SA on Day 5/90 Visit– Compliant Population
15.2.4.1.2	Descriptive Statistics of Blood COHb (%) – FAS
15.2.4.1.3	Descriptive Statistics of Blood COHb (%) – Compliant Population
15.2.4.2.2	Descriptive Statistics of MHBMA in 24-hour Urine Collection – FAS
15.2.4.2.3	Descriptive Statistics of MHBMA in 24-hour Urine Collection – Compliant Population
15.2.4.3.2	Descriptive Statistics of 3-HPMA in 24-hour Urine Collection – FAS
15.2.4.3.3	Descriptive Statistics of 3-HPMA in 24-hour Urine Collection – Compliant Population
15.2.4.4.2	Descriptive Statistics of S-PMA in 24-hour Urine Collection – FAS
15.2.4.4.3	Descriptive Statistics of S-PMA in 24-hour Urine Collection – Compliant Population
15.2.4.5.2	Descriptive Statistics of Total NNAL in 24-hour Urine Collection – FAS
15.2.4.5.3	Descriptive Statistics of Total NNAL in 24-hour Urine Collection – Compliant Population
15.2.4.6.1	Descriptive Statistics of Exhaled CO (ppm) – PP Set
15.2.4.6.2	Descriptive Statistics of Exhaled CO (ppm) – FAS
15.2.4.7.1	Descriptive Statistics of 1-OHP in 24-hour Urine Collection – PP Set
15.2.4.7.2	Descriptive Statistics of 1-OHP in 24-hour Urine Collection – FAS
15.2.4.8.1	Descriptive Statistics of Total NNN in 24-hour Urine Collection – PP Set
15.2.4.8.2	Descriptive Statistics of Total NNN in 24-hour Urine Collection – FAS
15.2.4.9.1	Descriptive Statistics of 4-ABP in 24-hour Urine Collection – PP Set
15.2.4.9.2	Descriptive Statistics of 4-ABP in 24-hour Urine Collection – FAS
15.2.4.10.1	Descriptive Statistics of 1-NA in 24-hour Urine Collection – PP Set
15.2.4.10.2	Descriptive Statistics of 1-NA in 24-hour Urine Collection – FAS
15.2.4.11.1	Descriptive Statistics of 2-NA in 24-hour Urine Collection – PP Set
15.2.4.11.2	Descriptive Statistics of 2-NA in 24-hour Urine Collection – FAS
15.2.4.12.1	Descriptive Statistics of o-tol in 24-hour Urine Collection – PP Set
15.2.4.12.2	Descriptive Statistics of o-tol in 24-hour Urine Collection – FAS
15.2.4.13.1	Descriptive Statistics of CEMA in 24-hour Urine Collection – PP Set
15.2.4.13.2	Descriptive Statistics of CEMA in 24-hour Urine Collection – FAS
15.2.4.14.1	Descriptive Statistics of HEMA in 24-hour Urine Collection – PP Set
15.2.4.14.2	Descriptive Statistics of HEMA in 24-hour Urine Collection – FAS

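### Do the time-point terms listed for nicotine and cotinine, or the mixed-model label on the sensitivity analysis, call for a change to the SAP?

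*SAP*

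**What the plan says.** SAP 12.6.2.2 begins its model description with "Nicotine and cotinine concentrations at each post-baseline timepoint will be analysed in the log space using an ANCOVA model". The terms that follow are log baseline, sex, daily cigarette consumption and "time point, product, and the interaction term between time point and product". It then says that the code printed in 12.6.1.3 "will be used for the analysis of nicotine and cotinine". That code contains the line "Model log_biomarker = log_baseline sex cigarette_cons" followed by randomization arm, and nothing that refers to time or to repeated records on a subject.

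SAP 12.6.1.3 says that the primary ANCOVA "will be repeated for the PP Set at Day 5 and Day 90 data by means of a mixed model approach". It names two departures from the primary analysis: missing values are not carried forward, and values outside the assessment windows are dropped. The primary analysis in 12.6.1.1 is coded with "Proc glm data=_data" and the same right-hand side. Section 12.6.2.1 adds that the sensitivity analyses "will be repeated for the biomarkers of exposure for secondary objectives", and the title of table 15.2.3.6 begins "Analysis of Additional Biomarkers of Exposure versus mCC and SA using Mixed Model on Day 5/90 Visit".

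**The concern.** A programmer cannot follow both the term list and the cited code in 12.6.2.2. The section also seems to conflict with itself, because a model fitted at one time point cannot estimate a time effect or a time-by-product interaction. If the visits were stacked instead, the code gives no within-subject covariance. A single product ratio averaged over visits would then have too narrow a confidence interval.

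In 12.6.1.3 the name suggests a repeated-measures model in which intermediate visits help with missing values. The code does nothing of the kind. A reader of tables 15.2.3.1.2 and 15.2.3.6 could believe that the carried-forward primary result had been checked against a longitudinal model when it had not.

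**Working it through.** The SAP gives no figure to reproduce here. The checks below use its model terms and visit schedule. The data are simulated, and the within-subject correlations are assumptions because the documents give none.

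**1. Terms side by side.** SAP 5.2 gives 8 post-baseline time points for plasma nicotine and cotinine (Days 1 to 5, 30, 60 and 90).

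| | Two arms | Three arms |
|---|---|---|
| Code in 12.6.1.3 (intercept, baseline, sex, consumption, arm) | 4 + 1 = 5 | 4 + 2 = 6 |
| Text of 12.6.2.2 fitted to all visits at once | 5 + 7 + 1×7 = 19 | 6 + 7 + 2×7 = 27 |

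Text and code do differ.

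**2. Fit at one time point, as the 12.6.2.2 sentence asks.** Time is constant, so its column repeats the intercept and the interaction column repeats arm. The design has 7 columns and rank 5, so the fitted space is unchanged. On 120 simulated subjects with the SAP's terms, the arm contrast was -0.72525, its standard error 0.07157 and the residual degrees of freedom 120 - 5 = 115, both with and without the two terms. SAS fits such rank-deficient models by a generalized inverse, so the arm ratio and its interval do not move.

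**3. Which reading the SAP supports.** Eight sections cite the 12.6.1.3 code: 12.6.2.2, 12.6.2.3, 12.6.2.4, 12.6.3.1.2, 12.6.3.1.3, 12.6.3.1.4, 12.6.3.2 and 12.6.3.3. Only 12.6.2.2 lists time terms. QSU-brief, MCEQ, MNWS and smoking topography are expressly analysed one time point at a time. As evidence of intent only, the Revision History (SAP 3.1) records that mixed-model code for nicotine and cotinine was withdrawn in favour of ANCOVA by time point. The two terms look like a remnant of that edit.

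**4. The less likely reading: stack all visits.** With a common residual within-subject correlation ρ, the standard error of the arm contrast averaged over 8 visits is understated by about √(1 + 7ρ):

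- ρ = 0.3: √3.1 = 1.76
- ρ = 0.5: √4.5 = 2.12
- ρ = 0.7: √5.9 = 2.43

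Simulation with the 12.6.2.2 terms, 80:40 subjects on Days 1 to 5 and 40:40 on Days 30, 60 and 90 (the per-protocol numbers assumed in SAP section 8) gave 1.72, 2.02 and 2.36. The factor falls if correlation is weaker between confinement and ambulatory visits. It is 1.51 in place of 1.72 with 0.3 within each setting and 0.1 across. It is 1.74 in place of 2.02 with 0.5 in confinement, 0.3 in ambulatory visits and 0.2 across. In the equal-correlation simulations, visit-specific contrasts from the same stacked fit rejected 4.5 to 5.8% of the time at a nominal 5%. The problem is therefore confined to a visit-averaged ratio.

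**5. The sensitivity analysis.** The primary analysis uses one Day 5 or Day 90 value per subject for each biomarker. With one record each and no RANDOM or REPEATED statement, REML estimates a single residual variance, RSS/(N - p), with the least-squares coefficients. On 114 simulated complete cases (114 - 5 = 109 residual degrees of freedom), both methods gave an arm effect of -1.26443 with standard error 0.09234. As printed, the analysis is the primary ANCOVA restricted to observed, in-window values.

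**The case for a change.** The best case for a change is that 12.6.2.2 says flatly that the code will be used, whereas six of the other seven sections say only that theirs will be similar. Its analysis tables (15.2.4.20.1 and 15.2.4.20.2) have titles covering the 90 days, and it promises one ratio, so a pooled estimate is not ruled out. Statisticians are unblinded once the SAP is final or the database is locked, whichever is later (SAP 6.3.2), so a choice left open could be made with arm data in view. For the primary endpoints, this sensitivity analysis is the planned check on carrying values forward, and the Day 30 and Day 60 urine data go unused in it.

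The mismatch of text and code stands, and so does the inexact label. The rest is weaker. The singular ratio is house style: 12.6.2.1 uses it for results on two days, and QSU-brief speaks of a single difference while analysing each time point. The opening sentence of 12.6.2.2 sets the unit of analysis, and on that reading no choice can alter a result. The section asks for means, a ratio and a 95% interval, with no p-value, threshold or gatekeeping, so false-positive rates have little bearing.

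On the label, 12.6.1.3 states both real differences from the primary analysis and prints the code; it does not claim to borrow from other visits. Adding a REPEATED statement would be a new analysis. For Day 90 it would need a rule on whose Day 30 and Day 60 data count, since the per-protocol set is defined period by period (SAP 10.2). No gain from it has been shown.

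**Conclusion.** No change follows. The two time terms in 12.6.2.2 are a clerical leftover that analysts will resolve sensibly: fitted at each time point, they leave the arm ratio, its standard error and its degrees of freedom as they were. The mixed-model name in 12.6.1.3 is loose, but the analysis is reproducible from the text and code and is a genuine observed-case, in-window contrast with the carried-forward primary result. Renaming it would change no number.

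This rests on reading 12.6.2.2 as separate fits by time point, which its own sentence and the parallel sections support, and on one record per subject in 12.6.1.3, which follows from the primary analysis although it is not said in words. The understatement of 1.72 to 2.36 fold belongs to a stacked, visit-averaged contrast with assumed equal correlations of 0.3 to 0.7, which the SAP does not clearly request. Only secondary and sensitivity analyses are involved; the primary ANCOVA and the success criterion are unaffected.

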12.6.2.3 Nicotine and Cotinine Pharmacokinetic Parameters

The parameters C_{peak} , C_{avg} and t_{peak} will be calculated on Day 5 as described in Section 7.2 "Pharmacokinetic Parameters". The data will be listed and summarized for both nicotine and cotinine.

The analysis will compare the log-transformed C_{peak} and C_{avg} on Day 5 between the THS 2.2 Menthol and mCC arms. An analysis of variance (ANOVA) model will be used with terms for sex, average daily mCC consumption over the last 4 weeks as reported during screening and randomization arm.

The SAS code will be similar to that described in Section 12.6.1.3 "Sensitivity Analysis", with no baseline value being included in the model.

LS means for each product along with the ratio (THS 2.2 Menthol : mCC) and 95% CI will be presented in the tables.

For t_{peak} on Day 5 the comparison between the THS 2.2 Menthol and mCC arms will be made by the Wilcoxon Rank Sum test using PROC NPAR1WAY in SAS. Median difference and 95% CI using the Hodges-Lehmann estimate will be tabulated.

The following code will be used:

```
Proc npar1way data=_data_ hl median;
  Class randomization_arm;
  Var tpeak;
  Run;
```

All summaries and analyses will be performed on the PP Set and FAS.

The data will be presented in the below outputs:

TFL number	Title
TABLES	
15.2.4.21.1	Descriptive Statistics of Plasma Nicotine and Cotinine PK Parameters on Day 5 – PP Set
15.2.4.21.2	Descriptive Statistics of Plasma Nicotine and Cotinine PK Parameters on Day 5 – FAS
15.2.4.22.1	Analysis of Plasma Nicotine and Cotinine PK Parameters on Day 5 – PP Set
15.2.4.22.2	Analysis of Plasma Nicotine and Cotinine PK Parameters on Day 5 – FAS
LISTINGS	
15.3.3.4	Listing of Nicotine and Cotinine PK Parameters on Day 5

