7.5.1.2 Plasma Nicotine and Cotinine

Nicotine and cotinine concentrations will be measured in plasma to evaluate the exposure to nicotine in all three study arms. No sampling for PK profile will be done for subjects in the SA arm (Day 5 to Day 6) and only one blood sampling will be done both on Day 5 and Day 6.

- On Day 0 to Day 4 (all study arms):

One blood sample per day will be taken in the evening between 08:00 PM-09:30 PM.

- Nicotine/cotinine Pharmacokinetic (PK) Profile on Day 5 and Day 6 (THS 2.2 Menthol and mCC arms only):

In total, nine blood samples will be drawn on Day 5. The first blood sample on Day 5 will be drawn within 15 minutes prior the first product use. On Day 5, the start time of the first product use (T_0) will serve as reference for the time to peak concentration. An additional eight blood samples will be drawn in 2 hour intervals after the start of product use. The last blood sample should be drawn no later than 11:00 PM, corresponding to the end of product use. At all time points, if the subject wants to use the product around the time of the blood draw, he/she should use it first and the blood will be drawn after product use. Depending on the time of the first product use, it may be that fewer than eight blood samples will be collected from a subject after T_0 .

On Day 6, two blood samples will be drawn. The first one will be 20 hours after T_0 and the second blood sample will be 24 hours after T_0 (with T_0 being the start time of first product use at Day 5).

- On Day 5 and Day 6 (SA arm only):

On Day 5, one blood sample will be drawn in will be taken in the evening between 8:00 PM-09:30 PM.

On Day 6, one blood sample will be drawn between 08:00 AM-09:30 AM.

- On Day 30 Visit (Day 30), Day 60 Visit (Day 60), Day 90 Visit (Day 90) (all study arms):

One blood sample will be drawn during these visits, irrespective of the time of product use.

Data and information contained in this document are considered to constitute trade secrets and confidential commercial information, and the legal protections provided to such trade secrets and confidential information are hereby claimed under the provisions of applicable law. No part of this document may be publicly disclosed without the written consent of Philip Morris Products S.A.

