**Table 13: Coefficients of Variation (ZRHX-EX-01 study)**

	THS 2.2 Menthol/mCC MR (CV)
COHb	0.44 (0.14)
3-HPMA	0.28 (0.20)
MHBMA	0.11 (0.47)
S-PMA	0.07 (0.50)

Abbreviations: 3-HPMA = 3-hydroxypropylmercapturic acid; CC = conventional cigarettes; COHb = carboxyhemoglobin; CV = coefficients of variation; MHBMA = monohydroxybutenyl mercaturic acid; MR = mean ratios; S-PMA = S-phenylmercapturic acid; THS 2.2 = Tobacco Heating System 2.2.

Based on these two sets of assumptions on the mean ratios and coefficients of variations for the four primary BoExp on Day 5, the power to demonstrate a reduction was computed. Subjects are expected not to have any reason for exclusion from the PP Set in the confinement period for THS 2.2 Menthol arm and in ambulatory and confinement condition for the mCC arm.

Fifty percent of the subjects are expected to be excluded from the PP Set in the THS 2.2 Menthol arm in the ambulatory (mostly due to lack of compliance to the randomized product). Thus the expected populations on which the reductions will be assessed as described in Table 14.

Table 14: Sample Size to Assess the Reductions

	Sample size to assess the reduction (THS 2.2 Menthol:mCC)
COHb	80:40
3-HPMA	80:40
MHBMA	80:40
S-PMA	80:40
Total NNAL	40:40

Table 15 describes the expected power to demonstrate a reduction on all 5 primary BoExps in smokers switching from mCC to THS 2.2 Menthol as compared to those continuing to smoke mCC, using one-sided test with 2.5% type I error probability using the assumptions from YVD-CS01-EU and ZRHX-EX-01 given a sample size of 160 smokers (~80 in THS 2.2 Menthol, ~40 in mCC, and ~40 in the SA arm).

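### Day 5 nicotine and cotinine Cpeak and Cavg are analysed without the Day 0 plasma level that the trial already collects: a small, avoidable loss of precision in a valid descriptive analysis

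*SAP*

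**What the plan says.** For the Day 5 pharmacokinetic parameters, SAP 12.6.2.3 states: "An analysis of variance (ANOVA) model will be used with terms for sex, average daily mCC consumption over the last 4 weeks", with randomization arm as the remaining term. It then says that the code follows the earlier section "with no baseline value being included in the model". No reason is given. The output is an estimate with an interval: "LS means for each product along with the ratio (THS 2.2 Menthol : mCC) and 95% CI will be presented in the tables". For tpeak a Wilcoxon rank sum test is used.

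The section just before it, SAP 12.6.2.2, treats plasma concentrations of the same two analytes differently. There, "Baseline is the assessment at 08:00 PM to 09:30 PM on Day 0", and the model is an "ANCOVA model with terms for log-transformed baseline concentration, sex, average daily mCC consumption over the last 4 weeks", plus time point, product and their interaction.

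The Day 0 sample comes from Protocol 7.5.1.2, which for Day 0 to Day 4, in all study arms, states: "One blood sample per day will be taken in the evening between 08:00 PM-09:30 PM". Serial sampling starts only on Day 5: "In total, nine blood samples will be drawn on Day 5", followed by two on Day 6.

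**The concern.** A pre-exposure level of the same analyte is a natural covariate for Day 5 nicotine and cotinine exposure. It may carry information on personal intake and metabolism that sex and cigarettes per day do not capture. If it is left out, that part of the between-subject variation stays in the error term. A chance difference between arms in baseline nicotine or cotinine then also carries into the THS 2.2 Menthol : mCC ratio, in proportion to the correlation.

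The two adjacent sections also sit awkwardly together. On Day 5, Protocol Table 15 schedules no plasma nicotine sample in the THS 2.2 Menthol and mCC arms apart from the serial ones. The Day 5 evening concentration in SAP 12.6.2.2 must therefore be one point of the profile that SAP 12.6.2.3 summarises. The point is adjusted for Day 0 and the summary of the profile is not. What is at stake is the width and stability of the ratios that describe how nicotine exposure from the product compares with that from menthol cigarettes.

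**Working it through.** **No stated figure to reproduce.** SAP section 8 and Protocol 12.2 give no power or precision for Cpeak or Cavg. The correlation needed is not in the documents either, so it is taken as an assumption over a range.

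**Inputs**
- Arm sizes: 80 THS 2.2 Menthol and 40 mCC, the numbers that SAP Table 14 expects for the Day 5 comparisons.
- Planned model: intercept, arm, sex, consumption. Residual df = 120 − 4 = 116; with one covariate added, 115.
- rho: partial correlation between the log Day 0 level and log Cpeak or Cavg after arm, sex and consumption. Assumed 0, 0.3, 0.5 and 0.7, with one slope common to both arms.
- CV of 50% for the outcome, assumed only to express results as ratios. Log-scale SD = √ln(1 + 0.5²) = 0.472.

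**Precision.** Variance of the arm contrast with the covariate, relative to without:

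VR = (1 − rho²) × (1 + 1/(115 − 1)) = (1 − rho²) × 1.0088

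The second factor is the cost of estimating the slope. Interval width changes by √VR − 1, and the equivalent sample-size multiplier is 1/VR.

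| rho | VR | Change in log-scale CI width | Equivalent n | Upper CI factor on the ratio (CV 50%) |
|---|---|---|---|---|
| 0 | 1.009 | 0.4% wider | × 0.99 | 1.199 → 1.200 |
| 0.3 | 0.918 | 4.2% narrower | × 1.09 | 1.199 → 1.190 |
| 0.5 | 0.757 | 13.0% narrower | × 1.32 | 1.199 → 1.171 |
| 0.7 | 0.514 | 28.3% narrower | × 1.94 | 1.199 → 1.139 |

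Break-even is where VR = 1: rho² = 1 − 1/1.0088 = 0.0087, so rho ≈ 0.09.

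**Chance imbalance.** The difference between arms in mean baseline has SD √(1/80 + 1/40) = 0.194 baseline SDs. Unadjusted, a k-SD imbalance multiplies the ratio by exp(k × 0.194 × rho × 0.472). For k = 1 this is 2.8%, 4.7% or 6.6% at rho 0.3, 0.5 or 0.7; for k = 2 it is 5.6%, 9.6% or 13.7%.

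**Check by simulation.** With 5,000 simulated trials at each rho, the SD of the adjusted estimate relative to the unadjusted one was 1.003, 0.959, 0.865 and 0.713 at rho 0, 0.3, 0.5 and 0.7. Both models were unbiased on average, and 95% interval coverage was 94.7% to 95.3%.

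**Fewer evaluable subjects.** SAP 7.2 calculates the parameters only when all samples are non-missing, while Protocol 7.5.1.2 expects that some subjects may give fewer than eight samples after first use. If such profiles count as incomplete, 80:40 is an upper bound. At 40:20, the imbalance SD is √(1/40 + 1/20) = 0.274, break-even rho is about 0.13, and the intervals are 3.7%, 12.6% or 27.9% narrower at rho 0.3, 0.5 or 0.7.

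**The case against.** The strongest reply is that no like-for-like baseline exists. Serial sampling is not done before Day 5, so nobody has a baseline Cpeak or Cavg. The other SAP models that adjust for baseline (primary biomarkers, CYP1A2, CYP2A6, risk markers, questionnaires, topography, and evening concentrations themselves) use the earlier value of the same variable. A reader might infer that SAP 12.6.2.3 breaks the SAP's own rule. It does not, and the protocol prescribes no model for these parameters.

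The proxy also has weaknesses:
- The Day 0 sample is timed by the clock, whereas on Day 5 a subject wanting to use product around a draw does so first and is then sampled.
- On Day 0 compatible cigarettes are smoked through the topography device, which is not scheduled on Day 5 (Protocol 7.8.2).
- Two thirds of the compared subjects (80 of 120) have changed product by Day 5, so a common slope is itself an assumption.
- Stratification and model terms for sex and consumption already remove part of what baseline would explain.

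Finally, Day 5 evening concentrations and 24-hour urinary nicotine equivalents are already analysed with baseline adjustment, so the nicotine comparison does not rest on this model alone.

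All of this stands as a limit on how large rho may be. It does not remove the point. A covariate need not be the same measure as the outcome; it must be unaffected by assignment and related to the outcome. The Day 0 evening sample precedes both disclosure of the arm and first use of the assigned product. A partial correlation above about 0.09 is enough to gain, and at zero the loss is 0.4% of interval width.

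**Conclusion.** The point holds as a missed gain in precision, of low severity. Its size rests on an assumed rho: from 0.4% wider at rho 0 to about 28% narrower at rho 0.7, at 80:40 with a common slope. The percentage shifts from imbalance rest on an assumed CV of 50% as well.

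Two stronger conclusions are tempting and not supported. One is that the planned ratios are biased or their intervals wrong. Allocation is randomised, the contrast comes from a linear model on the log scale, and the planned interval already allows for chance imbalance; the simulated coverage agrees. The other is that the omission costs power. The objective is to describe the profiles, and no test, margin or power is planned for Cpeak or Cavg, so any power figure would need an invented effect size.

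**What to change.** Before database lock, in SAP 12.6.2.3 replace "with no baseline value being included in the model" by: *with the log-transformed Day 0 evening (08:00 PM-09:30 PM) plasma concentration of the same analyte as covariate, as in Section 12.6.2.2*. Apply this to Cpeak and Cavg of nicotine and of cotinine, and leave the tpeak test unchanged. If the sponsor prefers to keep the ANOVA, the SAP should give the reason and add the adjusted model as a sensitivity analysis.

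The cost is one sentence, one model term and one degree of freedom. Because SAP 12.1.5 does not impute missing baseline values, any subject without a Day 0 evening value drops out of the adjusted model, as in SAP 12.6.2.2. That loss comes on top of the complete-profile rule in SAP 7.2, so the number analysed should be shown with each ratio. No new data are needed.
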